8.2.4 Further Analyses

Because of the small sample size and the comparatively high number of trial sites, no further analyses of effects of trial sites will be provided.

8.2.5 Sensitivity Analyses

Sensitivity analyses are planned for the stability investigation of the result of the confirmatory analysis of the primary endpoint. Patients who withdraw will be excluded from the confirmatory data analysis but will be analysed in a separate exploratory sensitivity analysis. Two distinct scenarios will be regarded to investigate the influence of withdrawals. In a first scenario is the primary endpoint in all withdrawals set to CR='no'. In the second scenario is the primary endpoint in all withdrawals set to CR='yes'.

Another sensitivity analysis is planned for patients with discrepancy between using the modified 2007 Cheson criteria and the data base entries regarding the evaluation of the primary endpoint. If there are such patients, two further scenarios for the primary endpoint will be investigated: In the first scenario the modified 2007 Cheson criteria will be applied, in the second scenario the data base entries as entered by the sites will be used.

8.2.6 Safety Analysis

Generally, safety evaluations include: adverse events and clinical laboratory parameters (hematology, serum chemistry, serum immunoglobulin (IgG, IgM, IgA), CRP). The severity of adverse events will be assessed using National Cancer Institute Common Terminology Criteria for Adverse Events, Version 5.0.

Analysis of adverse events (AE), serious adverse events (SAE) and adverse events of special interest (AESI): AEs, SAEs and AESIs will be listed in tabular form. Listings will be provided for all AEs, SAEs, AESIs, and for AEs of grade ≥ 3 , SAEs of grade ≥ 3 , AESIs of grade ≥ 3 . Furthermore, the proportion (incl. 95% confidence interval) of patients with at least one AE / SAE / AESI will be calculated.

Analysis of concomitant medication: The time course of concomitant medication will be provided for each patient as listing of main variables (*SUBJECTID*, *CMSPID*, *CMTRT*, *CMINDC*,

CMDSTXT, *CMFREQ*, *CMROUTE*, *CMROUTEOTH*, *CMSTDAT*, *CMONGO*, and *CMENDAT* in table **CM**) of each medication ordered by number of medication (variable *CMSPID* in table **CM**). **Analysis of clinical laboratory parameter (hematology, serum chemistry, serum immunoglobulin (IgG, IgM, IgA), and CRP):** For each of the parameters of hematology (hemoglobin, hematocrit, platelets, erythrocytes, leukocytes, neutrophils, lymphocytes), serum chemistry (potassium, LDH, ALT, AST, GGT, alkaline phosphatase, uric acid, and CRP), and immunoglobulin (IgA, IgG, IgM) the time course will be analysed descriptively in a separate table with results from descriptive statistics. There will be a separate row for each point in time (see CTP pages 106-110). Furthermore, for each parameter of haematology and serum chemistry the frequency of clinical significant ratings and not clinically significant ratings will be provided.

Analysis of ECG findings: The frequencies for 'Examination performed?' (yes/no) and result (negative/positive) will be calculated for each point in time. In case of a clinically significant result, the time course of the results in the respective patient will be listed (variable *EGORRES* in table **EG**). Additionally, the respective database record in table **MH1** will be listed in this case.

8.2.7 Medical history and concomitant diseases

The analysis of previous diseases and concomitant diseases is based on number of occurrences together with corresponding counts of patients. In all tables, counts and frequencies of occurrences together with corresponding counts of patients will be listed.

9 Listings, Tables, Figures

All results from statistical analyses will be provided by means of listings, tables and figures as Word file (*.docx) or RTF file (*.rtf).

10 Software

All statistical analyses will be performed using SAS, version 9.4 (SAS Inc. Cary/NC, USA) under Windows 10 or 11. SAS- macros developed at the Institute of Epidemiology and Medical Biometry will be used for analyses, if applicable. Some Figures will be created using R, version 4.5.0, as appropriate.

11 Use of Results of Statistical Analysis

Parts of the statistical analysis (e.g. tables, figures, and summary statistics) will be provided to the Comprehensive Cancer Center / Department of Internal Medicine III / Institute for Experimental Tumour Research for preparation of the Synopsis according to the ICH E3 guideline. The shorted clinical trial summary report and other scientific contributions (e.g. article, oral presentation, poster) will be prepared by the Comprehensive Cancer Center / Department of Internal Medicine III / Institute for Experimental Tumour Research. (At least) one employee from the Institute of Epidemiology and Medical Biometry will be mentioned as co-author in each scientific contribution. The employee will be informed about the content of each scientific contribution.

12 Appendices

12.1 Conversion Factors for Laboratory Units

The following tables show the units which will be used in the statistical analysis.

Hematology			
Value	unit for statistical analysis	value	unit for statistical analysis
Hemoglobin	g/dL	Leukocytes	/nL
Hematocrit	%	Neutrophils	/nL
Platelets	10 ⁹ /L	Lymphocytes	/nL
Erythrocytes	/pL		

Quantitative Immunoglobulins	
value	unit for statistical analysis
IgA	mg/dL
IgG	mg/dL
IgM	mg/dL

Serum chemistry			
Value	unit for statistical analysis	value	unit for statistical analysis
Potassium	mmol/L	GGT	U/L
LDH	U/L	Alkaline Phosphatase	U/L
ALT	U/L	Uric acid	μmol/L
AST	U/L	CRP	mg/L

Peripheral blood -/ Leukocyte Immunophenotyping (FACS) – Antigen expression of the lymphoma	
value	unit for statistical analysis
Kappa	mg/dL
Lambda	mg/dL
Kappa / Lambda ratio	-

Thyroid hormones	
value	unit for statistical analysis
Triiodothyronin (T3)	nmol/L
Thyroxin (T4)	nmol/L
Thyrotropin (TSH)	mU/L

Institute of Epidemiology and Medical Biometry

The following table shows the conversion factors which will be used for the conversion of the laboratory results in units that will be used in the statistical analysis.

Parameter Group	Parameter	Unit for statistical analysis	Actual unit	Conversion factor
Hematology	Hemoglobin	g/dL	mmol/L	1.61
Hematology	Hematocrit	%	L/L	100
Hematology	Platelets	10 ⁹ /L	x10 ³ /uL	1.000
Hematology	Platelets	10 ⁹ /L	10 ⁹ /L	1.000
Hematology	Platelets	10 ⁹ /L	/uL	0.001
Hematology	Platelets	10 ⁹ /L	/nL	1.000
Hematology	Erythrocytes	/pL	T/L	1.000
Hematology	Erythrocytes	/pL	/pL	1.000
Hematology	Leukocytes	/nL	x10 ³ /uL	1.000
Hematology	Leukocytes	/nL	/uL	0.001
Hematology	Leukocytes	/nL	/nL	1.000
Hematology	Leukocytes	/nL	10 ⁹ /L	1.000
Hematology	Leukocytes	/nL	Giga/L	1.000
Hematology	Neutrophils	/nL	%	Leukocytes
Hematology	Neutrophils	/nL	/uL	1.000
Hematology	Neutrophils	/nL	/nL	1.000
Hematology	Neutrophils	/nL	10 ⁹ /L	1.000
Hematology	Neutrophils	/nL	Giga/L	1.000
Hematology	Lymphocytes	/nL	%	Leukocytes
Hematology	Lymphocytes	/nL	10 ⁹ /L	1.000
Hematology	Lymphocytes	/nL	Giga/L	1.000
Serum chemistry	Potassium	mmol/L	mg/dL	0.256
Serum chemistry	LDH	U/L	ukat/L	60
Serum chemistry	ALT	U/L	ukat/L	60
Serum chemistry	AST	U/L	ukat/L	60
Serum chemistry	GGT	U/L	ukat/L	60
Serum chemistry	Alkaline phosphatase	U/L	ukat/L	60
Serum chemistry	Uric acid	µmol/L	umol/L	1.000
Serum chemistry	Uric acid	µmol/L	mg/dL	59.485
Serum chemistry	CRP	mg/L	mg/dL	10
Thyroid hormones	Triiodthyronin (T3)	nmol/L	ng/dL	0.0154
Thyroid hormones	Thyroxin (T4)	nmol/L	ug/dL	12.8722
Thyroid hormones	Thyreotropin (TSH)	mU/L	uU/mL	1.000

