Conversion of laboratory results: There is no standardized unit for the laboratory results (haematology, quantitative immunoglobulins, serum chemistry, thyroid hormones) in the data base (see annotated CRF at pages 105-113, 162f, 170-182, 186f). Therefore, the Comprehensive Cancer Center / Department of Internal Medicine III / Institute for Experimental Tumour Research will provide a table for the conversion of the laboratory results in units which will be used in the statistical analysis. These units are mentioned in the appendix (part 12.1). All conversion factors for units known at the time of finalization of this document are listed in the appendix (see part 12.1).

Harmonization of response categories for tumor assessment: For the statistical analysis of the primary endpoint and some secondary endpoints in the whole study population, a harmonization of the response categories for tumor assessment will be performed. This is due to the different response categories in the three subgroups (see annotated CRF at page 188ff, CTP at page 116ff). The response categories after the harmonization are complete remission (CR), partial remission (PR), stable disease (SD), progressive disease (PD) and not evaluated (NE). The appendix (part 12.2) shows the allocation of the single response categories.

Format of date variables: All date variables given in the database are strings in the format yyyy-mm-dd. In the statistical analysis, all date variables will be presented in the format dd/mm/yyyy.

General remarks: All data are stored in a data base provided by X-act Cologne Clinical Research GmbH. The data will be provided as SAS data (sas7bdat). No checks of plausibility and consistency will be carried out by the Institute of Epidemiology and Medical Biometry. All variables containing information for organisation, data entry, and data management are not mentioned in this document and will not be analysed. No English translation will be done in case of German data base entries.

7 Listing of Variables

The descriptive methods will be applied for whole study population. Additionally, a simple description will be performed for the MZL subtype strata MALT lymphoma, splenic MZL, nodal MZL instead subgroup analyses.

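### SAP 12.1 converts neutrophils from /uL to /nL with a factor of 1.000, which contradicts the table's own leukocyte and platelet rows; either the factor or the unit label is wrong

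*SAP*

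**What the plan says.** SAP section 6 explains that the database has no common unit for laboratory results. The clinical department therefore supplies a conversion table, and the factors known when the SAP was finalised are listed in section 12.1. That section sets /nL as the analysis unit for neutrophils and presents the factors as binding: "The following table shows the conversion factors which will be used for the conversion of the laboratory results".

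The rows that matter here are:

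- "Neutrophils /nL /uL 1.000"
- "Neutrophils /nL /nL 1.000"
- "Leukocytes /nL /uL 0.001"
- "Neutrophils /nL % Leukocytes"
- "Lymphocytes /nL % Leukocytes"

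Platelets from /uL to 10^9/L also carry the factor 0.001. Platelets and leukocytes each have a further row for x10^3/uL with factor 1.000; neutrophils have no such row.

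On data checks, the general remarks in section 6 state: "No checks of plausibility and consistency will be carried out by the Institute of Epidemiology and Medical Biometry". Sections 8.1 and 8.2.6 then plan a time-course table for each haematology parameter, neutrophils included. It has one row per time point, with mean, SD, quartiles, minimum and maximum, and plots where suitable.

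**The concern.** The table treats the same unit change in two ways. Going from /uL to /nL divides leukocytes by 1,000 and leaves neutrophils unchanged. Neutrophils are a subset of leukocytes, so a patient with both counts in /uL could be tabulated with about a thousand times more neutrophils than leukocytes.

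At stake are the numeric neutrophil summaries in the safety analysis. In a trial stopped at 22 patients, one patient on the wrong scale dominates the mean and SD and sets the maximum. A genuinely low count would move to the top of the range, so the minimum would no longer show it.

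**Working it through.** **Inputs.** The factors are from SAP 12.1. The 22 patients are from SAP 2.1 and 3. The counts in steps 4 to 6 are assumptions for illustration.

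**1. The correct factor.** 1 nL = 0.001 uL, so count per nL = count per uL × 0.001. The stated factor is 1.000, and 1.000 / 0.001 = 1,000. For example, 1,500 /uL is 1.5 /nL, but the table returns 1,500 /nL.

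**2. The table's own comparators.** Leukocytes /uL to /nL: 0.001. Platelets /uL to 10^9/L: 0.001, the same step because 10^9/L equals 1 /nL. Both agree with step 1; the neutrophil row does not.

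**3. Can another reading rescue 1.000?**

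- As a thousands separator: no. The /nL to /nL row is also 1.000, where it must mean one, and the table uses decimal points elsewhere (0.256 for potassium, 59.485 for uric acid).
- As a divisor: no. CRP from mg/dL to mg/L is 10 and leukocytes from /uL are 0.001; both are multipliers.
- As a correct factor under a wrong label: possible. 10^3/uL to /nL is 10^3 × 0.001 = 1. In that case the unit label is the error, so the row still needs correcting.

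**4. Effect of one patient in /uL.** Assume 21 patients at 3 /nL and one recorded as 3,000 /uL, which is also truly 3 /nL.

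- Mean = (21 × 3 + 3,000) / 22 = 3,063 / 22 = 139.2 /nL, against 3.0.
- With one of n values displaced by d, the sample SD is d / √n = 2,997 / √22 = 639, against 0.
- The maximum is 3,000 /nL. The median and quartiles stay at 3.

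**5. Range over the unknown number of patients.** Assume every true count is 4.0 /nL and k of 22 patients are recorded in /uL. Mean = (4,000k + 4(22 − k)) / 22.

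| k | Mean (/nL) |
|---|---|
| 0 | 4.0 |
| 1 | 185.6 |
| 3 | 548.9 |
| 5 | 912.2 |

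**6. A low count.** A value of 500 /uL is 0.5 /nL. The table returns 500 /nL, so it leaves the minimum and becomes a candidate for the maximum.

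**7. The percentage rows.** Absolute count per nL = (% / 100) × leukocytes per nL. With 60% and 6 /nL this is 3.6 /nL. The table names leukocytes as the factor and does not show the division by 100, although it writes the scale out elsewhere ("Hematocrit % L/L 100"). It also does not say that leukocytes must first be in /nL.

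**The case against.** Several points on the other side are sound.

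- **The wrong cell is not identified.** Platelets and leukocytes each have an x10^3/uL row with 1.000 and a /uL row with 0.001, while neutrophils have only /uL with 1.000. A dropped x10^3 in the label explains this as well as a mistyped factor. If the values are really in 10^3/uL, applying 0.001 would make them 1,000-fold too low and create false neutropenia. This stands, and it makes the fix conditional.
- **Neutropenia is not hidden.** A reader might infer that it would be. However, Protocol 11.2.8 makes a laboratory abnormality an adverse event when it needs treatment or a dose change or is clinically important. Protocol 11.2.2 has the investigator grade it, and SAP 8.2.6 lists all adverse events and those of grade 3 or higher. SAP 7.1 and 8.2.6 also report the sites' clinical-significance ratings for each haematology parameter. None of these uses the factor.
- **Detection is not excluded.** Section 6 rules out plausibility checks by the biometry institute only. The clinical department supplies the conversion table and receives the results (SAP 2.2, 6 and 11), and a maximum of 500 or 3,000 /nL would be conspicuous. What remains is that neither document requires anyone to check the converted values. Source data verification (Protocol 14.4) tests the entries, not the conversion.
- **The percentage rows are not a 100-fold error.** Multiplying 60 by 6 to get 360 /nL takes the entry literally. The word in that column is naturally read as shorthand for a percentage of leukocytes. Only the scaling is left unwritten.
- **The reach is narrow.** No test or endpoint uses converted neutrophils. The splenic response criteria in Protocol Appendix F mention a neutrophil count, but SAP 7.5 takes complete response from the recorded tumour assessment.

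**Conclusion.** The neutrophil /uL row is wrong as written, by unit arithmetic and by comparison with two other rows of the same table. For any value truly in /uL the error is exactly 1,000-fold. It is confined to the descriptive neutrophil tables and plots, where one affected patient in 22 would distort the mean, SD and maximum and could remove a low value from the minimum. The rows for /nL, 10^9/L and Giga/L are correct.

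The example figures (mean 139, SD 639) rest on assumed counts and one assumed /uL patient. Because section 12.1 lists the units known when the SAP was finalised, the row suggests that values labelled /uL exist, but the documents give neither their number nor their true scale. If all of them are in 10^3/uL, the converted values are right and only the label is wrong.

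**What to change.** 1. List the recorded neutrophil values labelled /uL. Their size will normally settle the unit: thousands point to /uL, single digits to 10^3/uL. Query the site where it does not.
2. If they are in /uL, change the factor to 0.001. If they are in 10^3/uL, correct the unit label and keep 1.000. If both occur, give each its own row, as the table does for leukocytes and platelets.
3. Run a simple range check on the converted values before the tables are produced, and name who does it.
4. As a clarification only, write the percentage rows for neutrophils and lymphocytes as value × leukocytes (/nL) / 100, with leukocytes converted first.

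The cost is a short look at the data, one corrected table entry (an extra row if both units occur), two clarified entries and about one line of code. No endpoint, test or analysis population changes.

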12.2 Allocation of response categories

The following table shows the allocation for the responses categories in the tumor assessment for the statistical analysis of secondary endpoints in the whole study group.

Subtype	Response category (subtype)	Harmonized response category
Extranodal gastric MALT lymphoma	CR / pMRD	CR
	PR / rRD	PR
	SD / NC	SD
	PD	PD
	Relapse	PD
	NE	NE
Splenic MZL		
	CR	CR
	PR	PR
	SD / No response	SD
	PD	PD
	NE	NE
Nodal MZL/extragastric MALT lymphoma		
	CR	CR
	PR	PR
	SD	SD
	PD	PD
	NE	NE
